3.4.4 Exploratory Outcome Measures

The exploratory outcome measures for this study are as follows:

- Status of PD-L1 expression and other exploratory biomarkers (e.g. but not limited to protein and genetic markers) in archival and/or freshly obtained tumor tissues and plasma collected pre-treatment and during treatment with Atezolizumab
- Association of PD-L1 expression and other exploratory biomarkers (e.g. but not limited to protein and genetic markers) with disease status and/or response or resistance to Atezolizumab
- Status of exploratory biomarkers in plasma (including but not limited to genetic markers and cytokines such as IFN-gamma) collected pre-treatment and during treatment/at progression/study discontinuation with Atezolizumab

Association of exploratory biomarkers in plasma with disease status and/or response or resistance to Atezolizumab, tumor immunobiology or tumor type

4. MATERIALS AND METHODS

4.1 PATIENTS

4.1.1 Inclusion Criteria

Patients must meet the following criteria for study entry:

1. Signed Informed Consent Form
2. Ability to comply with protocol
3. Male or female, 18 years of age or older.
4. Histologically documented solid tumors that are advanced (i.e. Stages III or IV disease) and:
 - meet one of the cohort specifications in Section [4.1.3](#)
 - have progressive disease at study entry
 - have received at least one line of prior systemic therapy or for which alternative therapy does not exist which is known to prolong survival.
5. Representative formalin-fixed paraffin-embedded (FFPE) tumor specimens in paraffin blocks (preferred) or, in exceptional cases, 15 freshly cut and unstained slides, with an associated pathology report (in local language), for central testing. Detection of tumor in the provided block (or slide) needs to be confirmed by the central pathology laboratory prior to study enrollment.
 - Only tissue from core needle, punch or excisional biopsy sample collection will be accepted. For core-needle biopsy specimens, at least three cores should be submitted for evaluation. Fine-needle aspiration, brushing, bone tissue, and lavage samples are not acceptable
 - Patients who do not have tissue specimens meeting eligibility requirements must undergo a biopsy during the screening period. Acceptable samples include core needle biopsies for deep tumor tissue (minimum three cores) or excisional, incisional, punch, or forceps biopsies for cutaneous, subcutaneous, or mucosal lesions
6. Measurable disease as defined by RECIST, v1.1. (except for prostate cancer and malignant pleural mesothelioma) and disease-specific criteria for patients with prostate cancer (see [Appendix 6](#)) and malignant pleural mesothelioma (see [Appendix 7](#))
7. ECOG Performance Status of 0 or 1
8. Adequate hematologic and end organ function, defined by the following laboratory results obtained within 3 days prior to the first study treatment (Cycle 1, Day 1):
 - Absolute neutrophil count (ANC) ≥ 1500 cells/ μ L (without granulocyte colony-stimulating factor support within 2 weeks before Cycle 1, Day 1)

- Lymphocyte count $\geq 500/\mu\text{L}$
- White blood cell counts $> 2500/\mu\text{L}$
- Platelet count $\geq 100,000/\mu\text{L}$ (without transfusion within 2 weeks before Cycle 1, Day 1)
- Hemoglobin $\geq 9.0 \text{ g/dL}$ (patients may be transfused or receive erythropoietic treatment to meet this criterion)
- Serum bilirubin $< 1.5 \times$ upper limit of normal (ULN), with the following exception:
Patients with known Gilbert disease who have serum bilirubin level $\leq 3 \times$ ULN may be enrolled
- Aspartate aminotransferase (AST), alanine aminotransferase (ALT) and alkaline phosphatase $\leq 2.5 \times$ ULN, with the following exceptions:
Patients with liver involvement: AST and/or ALT $\leq 5 \times$ ULN
Patients with liver or bone metastases: alkaline phosphatase $\leq 5 \times$ ULN
- Serum creatinine $\leq 1.5 \times$ ULN or creatinine clearance $\geq 30 \text{ mL/min}$ on the basis of the Cockcroft-Gault glomerular filtration rate estimation:
 $(140 - \text{age}) \times (\text{weight in kg}) \times (0.85 \text{ if female}) / 72 \times (\text{serum creatinine in mg/dL})$
- International normalized ratio (INR) and activated partial thromboplastin time (aPTT) $\leq 1.5 \times$ ULN. This applies only to patients who do not receive therapeutic anticoagulation; patients receiving therapeutic anticoagulation (such as low-molecular weight heparin or warfarin) should be on a stable dose
- Serum albumin level $> 3.2 \text{ g/dL}$

9. Women who are not postmenopausal (≥ 12 months of non-therapy-induced amenorrhea) or surgically sterile must have a negative serum pregnancy test result within 14 days prior to initiation of study drug

10. For female patients of childbearing potential, agreement (by patient) to use a highly effective form(s) of contraception that results in a low failure rate ($< 1\%$ per year) when used consistently and correctly, and to continue its use for 5 months after the last dose of Atezolizumab. Such methods include: combined (estrogen and progestogen containing) hormonal contraception, progestogen-only hormonal contraception associated with inhibition of ovulation together with another additional barrier method always containing a spermicide, intrauterine device (IUD): intrauterine hormone-releasing system (IUS), bilateral tubal occlusion, vasectomized partner (on the understanding that this is the only one partner during the whole study duration), and sexual abstinence. Oral contraception should always be combined with an additional contraceptive method because of a potential interaction with the study drug.

11. Life expectancy > 3 months

4.1.2 Exclusion Criteria

Patients who meet any of the following criteria will be excluded from study entry:

1. Malignancies other than disease under study within 5 years prior to Cycle 1 Day 1, with the exception of those with a negligible risk of metastasis or death (e.g., expected 5-year OS > 90%) treated with expected curative outcome (such as adequately treated carcinoma in situ of the cervix, basal or squamous cell skin cancer, localized prostate cancer treated surgically with curative intent, ductal carcinoma in situ treated surgically with curative intent)
2. Uncontrolled tumor-related pain
 - Patients requiring pain medication must be on a stable regimen at study entry
 - Symptomatic lesions amenable to palliative radiotherapy (e.g., bone metastases or metastases causing nerve impingement) should be treated prior to enrollment
 - Asymptomatic metastatic lesions whose further growth would likely cause functional deficits or intractable pain (e.g., epidural metastasis that is not presently associated with spinal cord compression) should be considered for loco-regional therapy if appropriate prior to enrollment
3. Uncontrolled pleural effusion, pericardial effusion, or ascites requiring recurrent drainage procedures (once monthly or more frequently)
 - Patients with indwelling catheters (e.g., PleurX) are allowed
4. Uncontrolled hypercalcemia ($> 1.5 \text{ mmol/L}$ ionized calcium or $\text{Ca} > 12 \text{ mg/dL}$ or corrected serum calcium $> \text{ULN}$) or symptomatic hypercalcemia requiring continued use of bisphosphonate therapy or denosumab
 - Patients who are receiving bisphosphonate therapy or denosumab specifically to prevent skeletal events and who do not have a history of clinically significant hypercalcemia are eligible
 - Patients who are receiving denosumab prior to enrollment must be willing and eligible to receive a bisphosphonate instead while on study
5. History of treated asymptomatic or symptomatic CNS metastasis or presence of CNS metastases as determined by CT scan or MRI evaluation during screening or at prior radiographic assessments.
6. Leptomeningeal disease
7. Spinal cord compression not definitively treated with surgery and/or radiation or previously diagnosed and treated spinal cord compression without evidence that disease has been clinically stable for ≥ 2 weeks prior to Cycle 1, Day 1
8. Any approved anticancer therapy, including chemotherapy, hormonal therapy or radiotherapy, within 3 weeks prior to initiation of study treatment; however, the following are allowed:
 - Hormone-replacement therapy or oral contraceptives
 - Palliative radiotherapy for bone metastases > 2 weeks prior to Cycle 1, Day 1

9. Acute toxicities from previous therapy that have not resolved to Grade ≤ 1, except for alopecia
10. Pregnant and lactating women
11. Evidence of significant uncontrolled concomitant disease that could affect compliance with the protocol or interpretation of results, including significant liver disease (such as cirrhosis, uncontrolled major seizure disorder, or superior vena cava syndrome)
12. Significant cardiovascular disease, such as New York Heart Association cardiac disease (Class II or greater), myocardial infarction within 3 months prior to Cycle 1, Day 1, unstable arrhythmias or unstable angina
 - Patients with a known left ventricular ejection fraction (LVEF) < 40% will be excluded
 - Patients with known coronary artery disease, congestive heart failure not meeting the above criteria, or LVEF < 50% must be on a stable medical regimen that is optimized in the opinion of the treating physician, in consultation with a cardiologist if appropriate
13. Severe infections within 4 weeks prior to Cycle 1, Day 1, including but not limited to hospitalization for complications of infection, bacteremia or severe pneumonia
14. Received oral or IV antibiotics within 2 weeks prior to Cycle 1, Day 1
 - Patients receiving prophylactic antibiotics (e.g., for prevention of a urinary tract infection or chronic obstructive pulmonary disease) are eligible
15. Major surgical procedure within 28 days prior to Cycle 1, Day 1 or anticipation of need for a major surgical procedure during the course of the study
16. History of severe allergic, anaphylactic, or other hypersensitivity reactions to chimeric or humanized antibodies or fusion proteins
17. Known hypersensitivity or allergy to biopharmaceuticals produced in Chinese hamster ovary cells or to any component of the Atezolizumab formulation
18. History of autoimmune disease, including but not limited to myasthenia gravis, myositis, autoimmune hepatitis, systemic lupus erythematosus, rheumatoid arthritis, inflammatory bowel disease, vascular thrombosis associated with anti-phospholipid syndrome, Wegener's granulomatosis, Sjögren's syndrome, Guillain-Barré syndrome, multiple sclerosis, vasculitis, or glomerulonephritis (see [Appendix 5](#) for a more comprehensive list of autoimmune diseases)
 - Patients with a history of autoimmune hypothyroidism on a stable dose of thyroid replacement hormone are eligible
 - Patients with controlled Type 1 diabetes mellitus on a stable insulin regimen are eligible

- Patients with eczema, psoriasis, lichen simplex chronicus, or vitiligo with dermatologic manifestations only (e.g., patients with psoriatic arthritis would be excluded) are permitted provided that they meet the following conditions:
 - Rash must cover less than 10% of body surface area (BSA).
 - Disease is well controlled at baseline and only requiring low potency topical steroids.
 - No acute exacerbations of underlying condition within the previous 12 months (not requiring PUVA [psoralen plus ultraviolet A radiation], methotrexate, retinoids, biologic agents, oral calcineurin inhibitors, high-potency or oral steroids)

19. Prior allogeneic bone marrow transplantation or prior solid organ transplantation

20. History of idiopathic pulmonary fibrosis (including pneumonitis), drug-induced pneumonitis, organizing pneumonia (i.e., bronchiolitis obliterans, cryptogenic organizing pneumonia), or evidence of active pneumonitis on screening chest CT scan

- History of radiation pneumonitis in the radiation field (fibrosis) is permitted

21. Any other diseases, metabolic dysfunction, physical examination finding or clinical laboratory finding giving reasonable suspicion of a disease or condition that contraindicates the use of an investigational drug or that may affect the interpretation of the results or render the patient at high risk from treatment complication

22. Positive test for HIV

23. Patients with active hepatitis B (defined as having a positive hepatitis B surface antigen [HBsAg] test at screening) or hepatitis C

- Patients with past hepatitis B virus (HBV) infection or resolved HBV infection (defined as having a negative HBsAg test and a positive antibody to hepatitis B core antigen [anti-HBc] antibody test) are eligible
- Patients positive for hepatitis C virus (HCV) antibody are eligible only if polymerase chain reaction (PCR) is negative for HCV RNA

24. Active tuberculosis

25. Signs or symptoms of infection within 2 weeks prior to Cycle 1, Day 1

26. Administration of a live, attenuated vaccine within 4 weeks prior to Cycle 1, Day 1 or anticipation that such a live attenuated vaccine will be required during the study

- Influenza vaccination should be given during influenza season only (example: approximately October to March in the Northern Hemisphere). Patients must not receive live, attenuated influenza vaccine (e.g., FluMist®) within 4 weeks prior to Cycle 1, Day 1 or at any time during the study treatment or within 5 months after the last dose of atezolizumab

27. Prior treatment with CD137 agonists or immune checkpoint blockade therapies, anti-PD-1, or anti-PD-L1 therapeutic antibodies

- Patients who have received prior treatment with anti-CTLA-4 may be enrolled, provided at least 5 half-lives (approximately 75 days) have elapsed from the last dose of anti-CTLA-4 to the first dose of Atezolizumab and there was no history of severe immune-mediated adverse effects from anti-CTLA-4 (NCI CTCAE Grade 3 and 4)

28. Treatment with systemic immunostimulatory agents (including but not limited to interferon-alpha (IFN- α) and interleukin-2 (IL-2) within 4 weeks or five half-lives of the drug (whichever is shorter) prior to Cycle 1, Day 1

29. Treatment with an investigational agent within 4 weeks prior to Cycle 1, Day 1 (or within five half-lives of the investigational product, whichever is longer)

30. Treatment with systemic corticosteroids or other systemic immunosuppressive medications (including but not limited to prednisone, dexamethasone, cyclophosphamide, azathioprine, methotrexate, thalidomide, and anti-tumor necrosis factor [TNF] agents) within 2 weeks prior to Cycle 1, Day 1, or anticipated requirement for systemic immunosuppressive medications during the trial

- Patients who have received acute, low-dose, systemic immunosuppressant medications (e.g., a one-time dose of dexamethasone for nausea) may be enrolled in the study
- The use of inhaled corticosteroids for chronic obstructive pulmonary disease, mineralocorticoids (e.g., fludrocortisone) for patients with orthostatic hypotension, low-dose supplemental corticosteroids for adrenocortical insufficiency and topical steroids for cutaneous diseases are allowed

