3. STUDY DESIGN

3.1 DESCRIPTION OF STUDY

This will be an open-label, multicenter, multinational, multicohort, phase II study. For each cohort, the study will consist of a Screening Period (Day -35 to -1), a Treatment Period, a Treatment Discontinuation Visit occurring \leq 30 days after the last dose of study medication and a 24-month Survival Follow-up Period ([Figure 1](#)). Day 1 (baseline) will be defined as the first day a patient receives study medication.

Figure 1. Study Schema

EOT end of treatment, EOS end of study

† Cohort closed to recruitment from Protocol Version 4 onwards

‡ Atezolizumab treatment may be continued as long as patients are experiencing clinical benefit (see Section 3.1, and Section 4.6.2).

The study will include 16 cohorts of patients with the following solid cancers:

1. Cervical cancer
2. Nasopharyngeal carcinoma
3. Known MSI-H- or MMR-deficient colorectal cancer
4. Known BRCA 1/2 mutated cancers
 - a. BRCA mutated ovarian cancer
 - b. BRCA mutated breast cancer
5. Soft tissue, visceral and bone sarcomas:
 - a. Liposarcoma
 - b. Leiomyosarcoma
 - c. Gastrointestinal stromal tumors (GIST)
 - d. Undifferentiated pleomorphic sarcoma
 - e. Known translocation-related sarcomas
 - f. Radiation induced sarcoma
 - g. Osteosarcoma
 - h Chondrosarcoma
6. Mesothelioma
 - a. Pleural mesothelioma
 - b. Peritoneal mesothelioma
7. Cholangiocarcinoma/cancer of the biliary tract
8. Thyroid cancer
 - a. Anaplastic thyroid cancer
 - b. Follicular or papillary thyroid cancer
 - c. Medullary thyroid cancer and mixed medullary and follicular or papillary thyroid cancer
9. Gastric adenocarcinoma/adenocarcinoma of the gastro-esophageal junction
10. Other solid tumors – closed to recruitment from Protocol Version 4 onwards
11. Malignant germ cell tumors
12. ER+/HER2- metastatic breast cancer with known high mutation load (>100 mutations) by local test

13. Thymoma and thymic cancer
 - a. Thymoma
 - b. Thymic cancer
14. Gastroenteropancreatic (GEP) and lung neuroendocrine tumors (NETs)
 - a. Low and intermediate grades (typical or atypical carcinoid)
 - b. Poorly differentiated grade (excluding SCLC)
15. Known HPV induced squamous cell carcinomas
 - a. Head and neck
 - b. Penile cancer
 - c. Vaginal cancer / vulvar cancer
 - d. Anal cancer
16. Known MSI high or MMR deficient tumors (excluding colorectal and gastric cancers)

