4.4 CONCOMITANT THERAPY

4.4.1 Permitted Therapy

Concomitant therapy includes any prescription medications or over-the-counter preparations used by a patient between the 7 days preceding the screening evaluation and the treatment discontinuation visit.

Patients who experience infusion-associated symptoms may be treated symptomatically with acetaminophen, ibuprofen, diphenhydramine and/or famotidine or another H2 receptor antagonist, as per standard practice (for sites outside the United States, equivalent medications may be substituted per local practice). Serious infusion-associated events manifested by dyspnea, hypotension, wheezing, bronchospasm, tachycardia, reduced oxygen saturation or respiratory distress should be managed with supportive therapies as clinically indicated (e.g., supplemental oxygen and β 2-adrenergic agonists).

Systemic corticosteroids and tumor necrosis factor- α inhibitors may attenuate potential beneficial immunologic effects of treatment with Atezolizumab but may be administered at the discretion of the treating physician. If feasible, alternatives to corticosteroids should be considered. Premedication may be administered for Cycles ≥ 2 at the discretion of the treating physician after consultation with the Medical Monitor. The use of inhaled corticosteroids for COPD and mineralocorticoids (e.g., fludrocortisone) and low-dose corticosteroids for patients with orthostatic hypotension or adrenocortical insufficiency is allowed. Megestrol administered as an appetite stimulant is acceptable while the patient is enrolled in the study.

Colony-stimulating factors, such as granulocyte colony-stimulating factor and erythropoietin, should only be used according to the ASCO and ASCO/ASH guidelines, respectively ([Smith et al. 2006](#); [Rizzo et al. 2010](#)). Influenza vaccination should be given during influenza season only (approximately October to March). Patients must not receive live, attenuated influenza vaccine (e.g., FluMist®) within 4 weeks prior to Cycle 1, Day 1 or at any time during the study treatment, or within 5 months after the last dose of Atezolizumab, but may receive inactivated vaccine.

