Patients who use hormonal therapy with gonadotropin-releasing hormone agonists or antagonists for prostate cancer, oral contraceptives, hormone-replacement therapy, prophylactic or therapeutic anticoagulation therapy (such as low molecular weight heparin or warfarin at a stable dose level), or other allowed maintenance therapy (see Section [4.1.2](#)) should continue their use.

Females of reproductive potential should use a highly effective means of contraception.

All concomitant medications should be reported to the investigator and recorded on the appropriate eCRF.

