4.4.2 Prohibited Therapy

Any concomitant therapy intended for the treatment of cancer, whether health authority-approved or experimental, is prohibited. This includes but is not limited to the following:

- Chemotherapy, hormonal therapy, immunotherapy, radiotherapy, investigational agents or herbal therapy (except for maintenance therapies outlined in Section [4.1.1](#), and [4.1.2](#))
 - After Cycle 2, certain forms of radiotherapy may be considered for pain palliation if patients are deriving benefit (e.g., treatment of known bone metastases). Please contact the Medical Monitor prior to initiating radiotherapy.
 - Patients experiencing a mixed response requiring local therapy (e.g., surgery, stereotactic radiosurgery, radiotherapy, radiofrequency ablation) for control of three or fewer lesions may still be eligible to continue study treatment. Patients who receive local therapy directed at a target lesion will no longer be evaluable for radiographic response but will remain evaluable for progression. Such cases must be discussed with and approved by the Sponsor

- The concomitant use of herbal therapies is not recommended because their pharmacokinetics, safety profiles, and potential drug-drug interactions are generally unknown. However, their use for patients on study is allowed at the discretion of the investigator, provided that there are no known interactions with any study treatment. As noted above, herbal therapies intended for the treatment of cancer are prohibited
- Patients who are receiving a receptor activator of nuclear factor kappa B ligand inhibitor (denosumab) prior to enrollment must be willing and eligible to receive a bisphosphonate instead while on study; denosumab could potentially alter the activity and the safety of Atezolizumab

Patients should not receive any live, attenuated vaccine (e.g., FluMist®) at any time during the study while the patient is receiving Atezolizumab and for a period of 5 months after the discontinuation of Atezolizumab.

Patients are not allowed to receive immunostimulatory agents, including but not limited to interferon (IFN)- α , IFN- γ , or IL-2, during the entire study. These agents, in combination with Atezolizumab, could potentially increase the risk for autoimmune conditions.

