4.6.2 Study Treatment Discontinuation

Patients must discontinue study treatment if they experience any of the following:

- Symptomatic deterioration attributed to disease progression as determined by the Investigator after integrated assessment of radiographic data, biopsy results, and clinical status
- Intolerable toxicity related to Atezolizumab, including development of an immune-mediated adverse event determined by the investigator to be unacceptable given the individual patient's potential response to therapy and severity of the event
- Any medical condition that may jeopardize the patient's safety if he or she continues on study treatment
- Use of another non-protocol anti-cancer therapy (see Section [4.4.2](#))
- Pregnancy

Atezolizumab treatment may be continued as long as patients are experiencing clinical benefit as assessed by an investigator in the absence of unacceptable toxicity or symptomatic deterioration attributed to disease progression after an integrated assessment of radiographic data, biopsy results (if available), and clinical status.

Patients will be permitted to continue Atezolizumab treatment after RECIST v1.1 (or disease-specific criteria for patients with prostate cancer [see [Appendix 6](#)] and malignant pleural mesothelioma [see [Appendix 7](#)]) criteria for progressive disease are met if they meet all of the following criteria:

- Evidence of clinical benefit as assessed by the Investigator
- Absence of symptoms and signs (including worsening of laboratory values, e.g., new or worsening hypercalcemia) indicating unequivocal progression of disease
- No decline in ECOG performance status that can be attributed to disease progression
- Absence of tumor progression at critical anatomical sites (e.g., leptomeningeal disease) that cannot be managed by protocol-allowed medical interventions

Patients treated with Atezolizumab in whom radiographic disease progression is confirmed at a subsequent tumor assessment may be considered for continued study treatment at the discretion of the Investigator if they continue to meet the above criteria.

If an individual patient continues to experience clinical benefit beyond 2 years of radiologic progressive disease, it lies within the discretion of each investigator to continue study treatment based on a positive risk benefit assessment by the investigator.

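### Exclusion 8 omits GnRH therapy for prostate cancer from its allowed list, although Section 4.4.1 tells those patients to stay on it

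*Protocol*

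**What the plan says.** Three places in the Protocol bear on the question.

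- **Entry (Section 4.1.2, exclusion 8, repeated in the synopsis).** A patient is excluded for "Any approved anticancer therapy, including chemotherapy, hormonal therapy or radiotherapy, within 3 weeks prior to initiation of study treatment". Two exceptions follow: "Hormone-replacement therapy or oral contraceptives", and palliative radiotherapy for bone metastases given more than 2 weeks before Cycle 1, Day 1.
- **Permitted therapy (Section 4.4.1).** "Patients who use hormonal therapy with gonadotropin-releasing hormone agonists or antagonists for prostate cancer" head a list of patients who are told to carry on with their treatment. The list ends with other maintenance treatment that is allowed, and refers the reader to Section 4.1.2.
- **Prohibited therapy (Section 4.4.2).** Concomitant cancer treatment is prohibited, including "Chemotherapy, hormonal therapy, immunotherapy, radiotherapy, investigational agents or herbal therapy (except for maintenance therapies outlined in Section" 4.1.1 and 4.1.2).

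The SAP says nothing on the matter.

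**The concern.** The entry rule and the permitted-therapy rule point in opposite directions for the same patient. A site that follows exclusion 8 to the letter would screen-fail a prostate cancer patient on a GnRH agent, or stop the agent for three weeks before the first dose. A site that follows Section 4.4.1 would enrol the patient and leave the agent in place. What is at stake is consistent eligibility decisions, and avoiding an interruption of cancer treatment that the Protocol elsewhere says to maintain. No estimate or test is at stake.

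**Working it through.** No arithmetic applies. The check sets the provisions side by side.

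1. **Does exclusion 8 cover GnRH therapy?** Yes. It names hormonal therapy as a form of anticancer therapy, and Section 4.4.1 itself describes GnRH agents as hormonal therapy for prostate cancer.
2. **Do its exceptions release it?** No. One concerns hormone replacement and contraception, the other bone radiotherapy.
3. **Does another entry criterion release it?** No. Section 4.1.1 provides for anticoagulation ("patients receiving therapeutic anticoagulation (such as low-molecular weight heparin or warfarin) should be on a stable dose"). Section 4.1.2 makes room for some bisphosphonate, thyroid-hormone and insulin use. Neither section mentions GnRH agents.
4. **What does Section 4.4.1 assume?** Only a patient already on an agent can carry on with it. By closing its list with *other* treatment that is *allowed*, and pointing to Section 4.1.2, the sentence places the treatments named before it, GnRH therapy included, among those already allowed. Section 4.1.2 does not contain the allowance that this presupposes.
5. **Can both rules be met at once?** Not without strain. Stopping for three weeks and restarting satisfies exclusion 8, but that is interruption and resumption, not continuation.
6. **Does Section 4.4.2 settle it?** No. Its exemption depends on Sections 4.1.1 and 4.1.2, so it inherits their omission. On study the specific permission in Section 4.4.1 is the natural reading, so this is an incomplete cross-reference and not a second conflict.
7. **Can such a patient arise?** Yes. Cohort 16 takes MSI-high or MMR-deficient solid tumors outside the colorectal and gastric sites (Section 4.1.3). Its rationale gives a 6.2% MSI frequency in prostate cancer (Section 1.3.1.16). Inclusion 6, PSA testing (Section 4.5.6) and Appendix 6 all provide for prostate patients. Cohort 10 has been closed since Protocol Version 4 (Section 1.3.1.10), which leaves Cohort 16 as the only route in.
8. **How many?** The documents give no count. The range runs from 0 to every prostate cancer patient screened for Cohort 16 while on a GnRH agent.

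**The case against.** The strongest reply is that Section 4.4.1 already resolves the question. It is the specific provision, it treats GnRH therapy as allowed, and the literal reading of exclusion 8 would leave its GnRH clause almost nothing to do. This stands as far as intent goes. A reader might infer that the Protocol leaves two equally open rules. The documents do not support that, because the wording of Section 4.4.1 shows which rule was meant. The reply does not repair the entry criterion, however. Section 4.1.2 excludes anyone who meets any listed criterion, and Section 4.4.1 does not say that it waives one. The offer in Section 4.4.2 to consult the Medical Monitor about unlisted medications can settle a single case but does not correct the rule.

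The second reply is that enrolment is probably over. Section 4.3.4 of Protocol Version 8 deals with the planned last visit and roll-over to an extension study. The SAP, Version 4.0 of 12 February 2020, reports in Section 4.1.1 that no enrolled patient went untreated, as a settled fact. Both suggest completed enrolment, though neither document says so. If it is complete, exclusion 8 affects no new patient. Section 4.4.2 would still apply to patients who remain on treatment until the extension study opens.

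Two further inferences are tempting but not supported:

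- Section 4.4.1 counts as concomitant any medication "used by a patient between the 7 days preceding the screening evaluation and the treatment discontinuation visit", a span that includes days before the first dose. This only defines which medications count as concomitant. It is not an eligibility rule and does not measure the conflict.
- Section 4.6.2 requires atezolizumab to stop for "Use of another non-protocol anti-cancer therapy", with reference to Section 4.4.2. A treatment that the Protocol tells patients to keep taking is not plainly non-protocol therapy, so the documents do not show that GnRH use would force discontinuation.

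**Conclusion.** The concern holds as a minor correction. Exclusion 8, in Section 4.1.2 and in the synopsis, literally bars a treatment that Section 4.4.1 says to continue and regards as already allowed. The intended rule is that GnRH therapy for prostate cancer is permitted; the error is an omission from the allowed list, carried into the cross-reference in Section 4.4.2.

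The reach is very small: only Cohort 16 prostate cancer patients on a GnRH agonist or antagonist, in unknown number and possibly none. The documents report no instance of sites acting inconsistently. The Simon design is untouched: 12 then 25 evaluable patients, with at least 3 and at least 8 non-progressors required. No analysis changes.

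The conclusion on intent rests on reading the closing words of the Section 4.4.1 list as covering the treatments named before them. The estimate of reach rests on Cohort 16 being the only open route for prostate cancer. Whether new patients can still be affected depends on the enrolment status of that cohort, which the documents do not state.

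**What to change.** With the next amendment:

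1. Add GnRH agonist or antagonist therapy for prostate cancer to the allowed list of exclusion 8 in Section 4.1.2.
2. Make the same addition in the synopsis.
3. In Section 4.4.2, name this therapy as an exception beside the reference to Sections 4.1.1 and 4.1.2.

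Section 4.4.1 can stay as it is. If Cohort 16 has finished enrolling, only the third edit is needed.

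The cost is three short text changes, or one, under the amendment approvals that Section 9.6 already requires. There are no added procedures, visits or patients, and the SAP needs no change.
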